#### Research question and objectives

The overall aim of the study is to describe how prescribing of NOMAC and CMA containing medicines (as single active ingredients and combinations with oestrogen) has changed following the EU-wide introduction of RMM in November 2022. To contextualise findings, changes in other relevant drug classes will also be described. This will include progestogen and oestrogen combination products and progestogens that are pregnadien derivates (see "Variables").

[figure not shown]
The specific objectives are:

- 1. To assess the monthly prevalence and incidence of use of drug classes of interest before and after the implementation of the restrictions of use.
- 2. To assess duration of use and cumulative dose of products containing NOMAC or CMA before and after the implementation of restrictions of use.
- 3. To describe characteristics of users of relevant drug classes before and after implementation of the restrictions of use.
- 4. To describe the line of treatment (2nd/3rd versus 1st) in users of products containing NOMAC or CMA before and after the implementation of the restrictions of use.
- 5. To describe the frequency of patients who develop meningioma during treatment with products containing NOMAC or CMA, and those who discontinue or switch to alternative treatments before and after implementation of the restrictions of use.
- 6. To assess the impact of the restrictions of use adopted in 2018 and 2022 in incident prescriptions of products containing NOMAC or CMA.

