#### Objective 5:

We will describe the frequency of switches of treatment with NOMAC or CMA to products of other relevant drug classes not containing NOMAC or CMA within 180 days after the end of treatment. We will also describe the number of patients discontinuing treatment. The number of meningioma cases occurring any time during treatment with NOMAC or CMA, and in the six months prior to treatment discontinuation will also be reported. Exposures of interest (NOMAC vs. CMA) will be assessed separately.

Results will be reported overall and stratified by study period and WHO 5th ATC level codes (if counts allow).

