In July 2022, PRAC issued further recommendations for both NOMAC and CMA. PRAC recommended to update the summary of product characteristics for products containing NOMAC or CMA to inform of the risk of meningioma. PRAC recommended that medicines containing high-dose chlormadinone (5 – 10 mg) or high-dose NOMAC (3.75 – 5 mg) should be used at the lowest effective dose and for the shortest duration possible. These medications should only be used when other interventions are not appropriate and should no longer be considered for first-line treatment. Similar to what was already established for NOMAC, treatment with products containing NOMAC or CMA was contraindicated in patients with current or prior history of meningioma. PRAC also recommended monitoring patients for symptoms, and permanently discontinuing treatment if the patients develop meningioma. (9) Measures recommended by PRAC were endorsed by the Committee for Medicinal Products for Human Use (CHMP) and the European Commission issued final legally binding decisions applicable in all the European Union (EU) Member States, between 28th of October and 28th November 2022.(10) Following this decision, a direct healthcare professional communication (DHPC) was sent to prescribers (8th November 2022)(11) and Marketing Authorisation Holders (MAH) had one month to implement changes (28th December 2022). Dates for national-level interventions varied, especially in the case of France, where additional interventions were put in place between 2018 and 2021.

The overall aim of the study is to describe how prescribing of NOMAC and CMA has changed following the introduction of risk minimisation measures (RMM) in November 2022. To contextualise findings, it is also of interest to study changes in prescribing of other relevant drug classes, including progestogen and oestrogen combination products and progestogens that are pregnadien derivatives, and to study the impact of prior EU-level restrictions in trends of NOMAC prescribing.

D2 C	2 000	Charles	Donate and
P3-C.	3-UU6	Stuav	Protocol

Version: V4.0

**Dissemination level:** Public

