## 7. RESEARCH QUESTION AND OBJECTIVES

The overall aim of the study is to describe how prescribing of NOMAC and CMA has changed following the introduction of EU-level RMM related to the risk of meningioma ('restrictions to use' from now on) in November 2022. To contextualise findings, changes of other relevant drug classes will also be described.

The specific objectives are:

- 1. To assess the monthly prevalence and incidence of use of drug classes of interest before and after the implementation of the restrictions of use.
- 2. To assess duration of use and cumulative dose of products containing NOMAC or CMA before and after the implementation of restrictions of use.
- 3. To describe characteristics of users of relevant drug classes before and after implementation of the restrictions of use.
- 4. To describe the line of treatment (2nd/3rd versus 1st) in users of products containing NOMAC or CMA before and after the implementation of the restrictions of use
- 5. To describe the frequency of patients who develop meningioma during treatment with products containing NOMAC or CMA, and those who discontinue or switch to alternative treatments before and after implementation of the restrictions of use.
- 6. To assess the impact of the restrictions of use adopted in 2018 and 2022 in incident prescriptions of products containing NOMAC or CMA.

Objective 1 and 3 will be assessed for all relevant drug classes. These will include progestogen and estrogen combination products, progestogens that are pregnadien derivates, and medroxyprogesterone-containing products.

Objective 2 and 6 will focus on products containing NOMAC or CMA. Objective 4 and 5 will focus on these two compounds but will consider relevant drug classes to establish line of treatment or switches.

A description of the proposed objectives is described in Table 1.

**Table 1.** Primary and secondary research questions and objective.

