## Objective 5:

[figure not shown]
We will describe the number and proportion of patients that follow different treatment strategies in the 180 days following the end of treatment. These strategies are defined as:

- Restart the same treatment
- Switch to a different treatment
- Restart and switch to a different treatment
   Discontinued treatment (not treated, neither with the original treatment nor any potential switch)

For this objective (time period comparison), both incident and prevalent users will be considered. The proportion of individuals following each treatment strategy (e.g. switching) will be calculated using the number of people exposed to the product of interest during the time period under study (e.g. pre-intervention) as the denominator regardless of when the initiation started.

Figure 2 illustrates some of these scenarios.

**Figure 2.** Outcomes after the drug exposure of interest (in blue) over different time periods.

Source: DrugUtilisation R package website (22)

The number of meningioma cases occurring any time during treatment with NOMAC or CMA, and in the six months prior to the end of treatment will also be reported. For cases identified in the six months prior, we will report the treatment strategy followed after treatment (i.e. restart, switch, both, or discontinuation).

NOMAC and CMA will be assessed separately. Results will be reported overall and stratified by study period (pre- vs. postintervention) and WHO 5th ATC level codes (if counts allow). For the pre- and post-intervention comparison, treatments initiated during the 180 days before the intervention will not be considered, to ensure sufficient time for assessing outcomes (e.g., switches, discontinuations) prior to the intervention.

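### Objective 5 reports what happens after meningioma only for women whose treatment ended within six months of diagnosis, so read as compliance with the stop-on-meningioma measure it overstates stopping

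*Protocol*

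**What the plan says.** Protocol Section 6 describes the 2022 recommendations, among them "PRAC also recommended monitoring patients for symptoms, and permanently discontinuing treatment if the patients develop meningioma". Section 7 gives the aim of Objective 5 in descriptive terms, beginning "To describe the frequency of patients who develop meningioma during treatment with products containing NOMAC or CMA", and adds discontinuation and switching.

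Section 8.8, Objective 5, then fixes three things about meningioma:

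- Count A, all cases on treatment: "The number of meningioma cases occurring any time during treatment with NOMAC or CMA".
- Count B, a look-back count: cases "in the six months prior to the end of treatment will also be reported". The Abstract words the window slightly differently ("and in the six months prior to treatment discontinuation will also be reported"), but it too is tied to treatment having ended.
- A follow-on readout for count B only: "For cases identified in the six months prior, we will report the treatment strategy followed after treatment". The categories are restart, switch, both, or discontinuation, assessed over 180 days from the end of treatment.

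The general strategy proportions in the same section use everyone exposed in the period as denominator. The paragraph on Objectives 2-5 plans standardised mean differences for meningioma on treatment and for discontinuing or switching, as separate items. Under All objectives, counts below 5 are masked.

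**The concern.** The natural question about this measure is: of the women diagnosed while on NOMAC or CMA, how many stopped and stayed off? The planned readout starts at the other end. It takes women whose treatment has ended, keeps those diagnosed in the preceding six months, and asks what they did next. Entry depends on having stopped, which is the behaviour of interest. The clearest departure from the measure, treatment that runs on well past diagnosis, is left out of the readout by construction. A woman treated for five months after diagnosis is in it and looks the same as one who stopped at once.

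At stake is the interpretation of the one table that a reader would turn to in order to judge whether treatment stops after meningioma. There is a second trap: better stopping moves more cases into count B, so B on its own can rise when the measure works.

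**Working it through.** The protocol gives no figure to reproduce here. Section 8.7 states that no sample size calculation was made, and no compliance proportion is defined.

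**1. Is the question answered elsewhere?**

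- Objective 1, meningioma subgroup: runs from diagnosis, but covers all women with meningioma, users or not, and is reported only overall and by calendar year.
- Objective 3: years since meningioma at the start of treatment, which bears on the contraindication and not on stopping.
- Objectives 2-5 standardised mean differences: meningioma and discontinuation or switching are never joined.

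None of these follows women forward from diagnosis.

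**2. Size of the difference.** Let s be the share of on-treatment cases whose treatment ends within six months of diagnosis, and r the share of those who restart NOMAC or CMA within 180 days. Switching to a product without NOMAC or CMA counts as having stopped.

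- Look-back readout: 1 - r
- Among all diagnosed women: s(1 - r)
- Ratio: 1/s. Difference: (1 - r)(1 - s)

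With r = 0.1 and a range of s, all assumed:

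| s | Look-back | All diagnosed | Difference (points) | Ratio 1/s |
|---|---|---|---|---|
| 1.0 | 90% | 90% | 0 | 1.00 |
| 0.9 | 90% | 81% | 9 | 1.11 |
| 0.8 | 90% | 72% | 18 | 1.25 |
| 0.5 | 90% | 45% | 45 | 2.00 |
| 0.3 | 90% | 27% | 63 | 3.33 |

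The look-back figure does not move with s. The difference is never negative. It is zero if nobody continues beyond six months (or, trivially, if everyone who ended restarts).

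**3. What the two counts recover.** Take an assumed A = 20 and B = 12, with 10 of the 12 discontinued and 2 restarting or switching. Then A - B = 8 is the number who continued beyond six months, and B/A = 12/20 = 60% is a crude stop-within-six-months share. If both of the other two restarted, the readout shows 10/12 = 83% stopped, against 10/20 = 50% of all diagnosed women. If both switched, it is 12/12 = 100% against 12/20 = 60%. The ratio is 1/0.6 = 1.67 either way. A, B and the 10 discontinuers are all above the masking limit, so the check works here. With smaller counts it may not.

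**4. Post-intervention window.** The period starts in February 2023 (Section 8.6.3); data locks are in Table 3. Days are counted inclusively from 1 February 2023.

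| Database | Lock | Days | Diagnosis days with 180 days after (days - 180) |
|---|---|---|---|
| Germany | 30-09-2023 | 242 | 62 |
| Croatia | 17-11-2023 | 290 | 110 |
| Belgium | 31-12-2023 | 334 | 154 |

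Objective 5 does not say how treatment still running at the end of data is classed, and B/A is sensitive to this. In a simulation of the 242-day German window, half of the cases were assumed to stop promptly (mean 30 days) and half to continue (mean 540 days). The underlying share stopping within 180 days of diagnosis was 64%. The share of cases entering the readout was 53% if only real treatment ends count, and 91% if the end of data counts as an end. These stopping times are assumptions.

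**The case against.** The strongest reply is that the protocol makes no claim about adherence. Objective 5 is descriptive, its hypothesis concerns switches and discontinuations among all users, and the planned standardised mean differences do not use the look-back readout. So no estimate exists to be biased; the overstatement arises only if the table is read as compliance. That stands, and it limits the weight of the point.

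Three stronger readings are tempting, and the documents do not support them.

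- A reader might infer that the long continuers are lost. They remain in count A, and A - B gives their number when cells are not masked.
- A reader might infer that the readout cannot show non-adherence. Restart, and restart with switch, are reported categories, and both mean NOMAC or CMA resumed after a diagnosis.
- A reader might count only the discontinued category as having stopped. A switch in this protocol is to a product without NOMAC or CMA, so a woman who switches has stopped the drug in question.

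The worry that a rising B would be taken for more meningioma is also partly met, because A is reported beside it and the standardised mean difference uses all cases during treatment.

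Finally, a diagnosis-anchored table will be sparse. Section 11 puts meningioma counts in the hundreds in most databases before any restriction to women on treatment, and says that studying the effect of the restrictions in that population will not be feasible. Masking would affect the new table too. This is a fair limit on what the fix can deliver, but not a reason to keep only a readout from which long continuation is excluded by design.

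**Conclusion.** The point holds in a limited form. The post-meningioma strategy is reported only for women whose treatment ended within six months of diagnosis, and no planned analysis reports stopping from the date of diagnosis. Used to judge the measure, the readout overstates stopping by a factor of 1/s. The documents give neither s nor r, so the actual size is unknown, and its effect on the pre/post contrast is undetermined. The comparison of B with A is a useful rough check, but it is not planned, it may be masked, and in the short post-intervention window it depends on an unstated rule for treatment running at the end of data.

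This is a worthwhile, inexpensive improvement to a descriptive table. It does not alter any standardised mean difference or stated hypothesis and is not a must-fix.

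**What to change.** Add a diagnosis-anchored readout to Section 8.8, Objective 5. Among women exposed to NOMAC or CMA when meningioma is first recorded, report from the diagnosis date:

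- (a) the number with any further NOMAC or CMA prescription;
- (b) the share with NOMAC or CMA ended and not restarted by 180 days, counting a switch to a product without either substance as ended.

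State how many women are censored before 180 days, and do not treat the end of data as the end of treatment. Report by period where counts allow, otherwise overall. Keep the look-back count and its strategy breakdown as a secondary description.

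The cost is code only, since the present counts already need the diagnosis and prescription dates. The downsides are few cases and heavy censoring after the intervention: only 62 to 154 days of diagnosis dates, depending on the database, have 180 days of data behind them, so the post-intervention cell may be masked or have to be pooled.

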#### **Covariates for stratification:**

Covariates for stratification will vary across objectives and will include:

- Age group:
   10-17, 18-34, 35-49, 50-64, +65 years.
- Indication:

Non-HRT vs. HRT. Indication will be assessed using age as a proxy (non-HRT in women aged 10-49 years, HRT in women aged >50 years).

- Dose:
  - High- vs low- dose, for NOMAC or CMA only. For NOMAC, high doses will include amounts from 3.75mg to 5mg. For CMA, high doses will include amounts from 5mg to 10mg. Low doses will be any amounts less than those specified.
- WHO 5th ATC level codes:
  - For NOMAC or CMA only, if counts allow. For NOMAC codes included will be: G03AA14, G03DB04, G03FB12. For CMA, codes included will be: G03AA15, G03AB07, G03DB06, G03FB03.
- Time period:
  - Preintervention: from start date to October 2022; Postintervention: from February 2023 to study end.

See below which covariates apply according to each objective.

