Concomitant medications	Large-scale characterisation and pre-specified medications 	Binary	[-365, -31], [-30,-1], 0	IP, OP	RxNo rm		New users of drug classes of interest or progestogens (objective 3)
Time period	Preintervention: January 2010 (or study start) to October 2022 Postintervention: February 2023 to end of available data	Categorical	N/A	IP, OP	N/A	N/A	All.

<sup>1IP = inpatient, OP = outpatient

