#### A. Primary analysis

Hypothesis:	Objective 1: Not applicable, descriptive analysis.
	Objective 2: Cumulative dose and duration of treatments with NOMAC or CMA will be lower after the implementation of restrictions.
	Objective 3: The number of new users of NOMAC or CMA with prior history of meningioma will be reduced after the implementation of restrictions.
	Objective 4: The number of users initiating NOMAC or CMA as first-line treatment will be reduced after the implementation of restrictions.
	Objective 5: The number of discontinuations and switches from NOMAC or CMA to other drug classes will increase after the implementation of restrictions.
	Objective 6: The incidence of NOMAC or CMA will be reduced after the implementation of restrictions, especially for high-dose products. This reduction will not be observed for other drug classes of interest.
Exposure contrast:	Objective 1: Not applicable, descriptive analysis.
	Objective 2: Pre-intervention (1-year period) vs. Post-intervention (1-year period)
	Objective 3 to 6: Pre-intervention vs. Post-intervention
Outcome:	Objective 1: Incidence rates and prevalence of drug classes of interest
	Objective 2: Cumulative dose and treatment duration of NOMAC or CMA.

Authors: [name], [name], [name], [name], [name]

Version: V4.0

Dissemination level: Public

	Objective 3: Number and characteristics of users of drug classes of interest.
	Objective 4: Line of treatment when initiating NOMAC or CMA.
	Objective 5: Diagnosis with meningioma during treatment. Discontinuations and switches
	from treatments with NOMAC or CMA to others.
	Objective 6: Incidence rates of NOMAC or CMA.
	Drug classes of interest, NOMAC and CMA will be assessed separately.
Analytic software:	R
Model(s):	Objective 1: Not applicable, descriptive analysis.
	Objective 2 to 5: Standardised mean differences.
	Objective 6: Segmented regression (Poisson models).
Confounding adjustment method	
	Stratification.
Missing data methods	
	The absence of a record for a condition or medication will be considered as the absence of the disease or use of the medication.
Subgroup Analyses	
	Objective 1: Age groups, indication, study period. For NOMAC or CMA only: dose, WHO ATC 5 th level (if counts allow). A subgroup analysis will be performed restricting the study population to individuals with a prior history of meningioma.
	Objective 2: Study population, indication, study period.
	Objective 3: Study period.

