#### **Databases:**

In IQVIA LPD Belgium and IQVIA DA Germany, the observation period of the patients in these databases is calculated based on the last visit, observation or interaction of the patient with the health care system. This methodology impacts the individuals considered "at risk" for the different medicines of interest of the study (i.e., the individuals included in the denominator populations) during the latest months of available data from the latest data lock, where healthy and/or non-frequent users of the health care system will not be considered active. Consequently, the denominators that will be used to calculate the incident use of drugs in the population may present an artefactual decrease whilst the incident users will remain, incrementing the incidence and prevalence ratios. The presence of these artefacts will be considered when interpreting the results. However, this is likely to affect the amount of follow up available for the study. We expect that the data from the last 6 months may not accurately reflect actual figures of use and, therefore, will be excluded from the analysis for Objective 1 and 6.

Regarding the study period, NAJS will provide data from 2017 onwards only, as prior data might include information on duplicated patients. IQVIA LPD Belgium will provide data from 2012 onwards.

Since information on drug exposure end dates is unavailable in NAJS, treatment duration will not be inferred directly from the start and end dates of drug exposure. Instead, we will infer the treatment period using only the drug exposure start dates, assuming continuous drug exposure between consecutive start dates, if separated by less than 90 days. To account for the final prescription, we apply a 30-day window following the last recorded drug start date. This approach might lead to some uncertainty regarding the exact duration or cumulative dose prescribed.

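### Objective 5 compares proportions of all exposed users over very unequal periods, with no rule for 180-day windows cut off at data lock, so a pre/post difference would appear without any true change

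*Protocol*

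**What the plan says.** Section 8.8, Objective 5, sorts patients into restart, switch, both, or discontinued, according to the 180 days after the end of treatment. For the period comparison it includes incident and prevalent users and computes each proportion "using the number of people exposed to the product of interest during the time period under study (e.g. pre-intervention) as the denominator", whenever treatment began. It adds that "treatments initiated during the 180 days before the intervention will not be considered, to ensure sufficient time for assessing outcomes" before the intervention.

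The periods are the general ones of section 8.6.3: "Preintervention: from start date to October 2022; Postintervention: from February 2023 to study end". Table 9 applies the same definition to all study populations. Section 11 sets later starts for two databases: "IQVIA LPD Belgium will provide data from 2012 onwards" and "NAJS will provide data from 2017 onwards only". Table 3 lists data locks of 30 September 2023 (Germany), 31 December 2023 (Belgium) and 17 November 2023 (NAJS).

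The pre and post proportions are compared by standardised mean difference (SMD), including the proportion with meningioma during treatment. Table 11 states the hypothesis: "The number of discontinuations and switches from NOMAC or CMA to other drug classes will increase after the implementation of restrictions".

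Two protections exist elsewhere but not here. Objective 2 uses periods of equal length covering the same calendar months. Section 11 drops the last six months of data for Objectives 1 and 6 only.

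**The concern.** The outcome clock starts when treatment ends, but the protective exclusion uses the date treatment starts. A treatment begun before the cut-off can still end, or have its 180 days run, after November 2022. The rule therefore does not secure its stated aim of assessing outcomes before the intervention.

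At the other end, nothing removes post-period treatments that end within 180 days of data lock. Dividing by all exposed users adds a second asymmetry. Over many years almost every user has a recorded treatment end; over 8 to 11 months many are still on treatment. These features alone would produce an SMD that a reader of the report would take as an effect of the restrictions.

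**Working it through.** The plan gives no precision or sample size figure for Objective 5, so there is none to reproduce. The check uses calendar arithmetic on the stated dates, then a no-change calculation with labelled assumptions.

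**1. Period lengths and complete windows.** A post-period treatment end has a full window if it falls on or before lock minus 180 days.

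| | Germany | Belgium | NAJS |
|---|---|---|---|
| Pre-period (months to Oct 2022) | 154 | 130 | 70 |
| Post-period days (1 Feb 2023 to lock) | 242 | 334 | 290 |
| Post-period months | 8.0 | 11.0 | 9.5 |
| Last end with a full window | 3 Apr 2023 | 4 Jul 2023 | 21 May 2023 |
| Days allowing a full window | 62 | 154 | 110 |
| Share without a full window | 180/242 = 74% | 180/334 = 54% | 180/290 = 62% |

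The shares assume treatment ends spread evenly over the post-period. By contrast, a treatment ending on 31 October 2022 has its 180 days by 29 April 2023, before every lock.

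**2. The start-date exclusion.** 180 days before 1 November 2022 is 5 May 2022. A treatment begun on 15 April 2022 and lasting 60 days is kept, yet its window closes on 11 December 2022. In the simulation below, 2–16% of pre-period users have windows that do not close before November 2022. This is the smaller part of the problem.

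**3. Switching with no true change.** Assumptions: constant initiation; exponential treatment length with mean 90, 180 or 365 days; true 180-day switch probability 20%; switch delays exponential with scale 60 days, truncated at 180; no restarts or loss to follow-up.

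| | Switching, pre | Switching, post | SMD |
|---|---|---|---|
| Germany | 19–20% | 6–11% | -0.25 to -0.39 |
| Belgium | 19–20% | 8–13% | -0.18 to -0.32 |
| NAJS | 18–20% | 7–13% | -0.20 to -0.33 |

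Restricted to ended treatments, the SMD is about -0.07 to -0.12. Most of the distortion therefore comes from the all-exposed denominator, the rest from cut-off windows.

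**4. Discontinuation with no true change.** Assume a true 180-day value of 50%, a constant restart/switch hazard h = ln 2/180, and that a cut-off window without a later record counts as discontinued. Among ended treatments the observed post value is the mean of exp(-h·min(u,180)) over the days u from treatment end to lock: 67% (Germany), 62% (Belgium), 64% (NAJS). That is upward.

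The plan divides by all exposed, so this must be multiplied by the share ended. With constant initiation and mean length D, the share ended in T days is T/(T+D). For Germany, T = 242:
- D = 30 days: 242/272 = 0.89; 0.89 × 0.67 = about 0.59
- D = 90 days: 242/332 = 0.73; 0.73 × 0.67 = about 0.49
- D = 365 days: 242/607 = 0.40; 0.40 × 0.67 = about 0.27

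The pre-period value is about 0.48 to 0.50 (share ended 0.95 to 1.00 for D from 365 to 90 days, times 0.50). For users already on treatment on 1 February 2023 alone, the share ended is 1 - exp(-T/D), giving 0.93 × 0.67 = 0.62 at 90 days and 0.49 × 0.67 = 0.33 at 12 months. On either calculation the sign depends on treatment length.

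**5. Later locks.** If each lock moved one year later (an assumption), the full-window shares would be 428/608 = 70%, 520/700 = 74% and 476/656 = 73%.

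**The case against.** Several limits stand.

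- A reader might infer that the bias favours the hypothesis, or that follow-up time alone decides the result. The documents do not support either. Switching is biased against the hypothesis. The upward shift in discontinuation is among ended treatments, whereas the plan divides by everyone exposed. The sizes rest on treatment lengths and hazards that the protocol does not give.
- A reader might also infer that every pre-period window is complete. It is so only with respect to data lock. Section 8.4 stops follow-up when observation ends, and section 11 says that observation in the German and Belgian databases ends at the last contact.
- Counting a cut-off window as discontinued is an inference. It rests on the definition of discontinuation as not being treated (section 8.8) and on the rule in Table 11 that an absent record means no use. The protocol does not state it for censored windows.
- The Table 3 locks are those of the last update, while the code is to run in March/April 2025 and the one-year comparison of Objective 2 runs to January 2024. Later locks could turn the majority of incomplete windows into a minority, but the asymmetry would remain.
- Objective 5 is descriptive, with no test or threshold. The SMD is nevertheless presented as a measure of impact, against a directional hypothesis.

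The limitation in section 11 about long-term effects does not cover any of this.

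**Conclusion.** The point holds. Followed exactly, the plan yields a pre/post difference in Objective 5 when prescribing has not changed. Under the stated assumptions the switching SMD is about -0.18 to -0.39, against the hypothesis. For discontinuation, truncation pushes upward (if cut-off windows count as not treated) and unended treatments push downward, so the net sign is undetermined. The proportion with meningioma on treatment compares groups with unequal exposure time and cannot be read as a change in risk or in practice. The day counts follow from the document's own dates; the 74%, 54% and 62% rest on the Table 3 locks and an even spread of treatment ends.

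**What to change.** Anchor the pre/post comparison of Objective 5 on the treatment end date:

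- **Post:** ends from 1 February 2023 to data lock minus 180 days.
- **Pre:** the same calendar dates in an earlier year, with end plus 180 days no later than 31 October 2022. At the listed locks Germany can use 2022 (3 April + 180 days = 30 September). Belgium (4 July + 180 days = 31 December) and NAJS (21 May + 180 days = 17 November) need 2021 or earlier, where the protocol's own COVID-19 caveat for 2021 applies.
- **Denominator:** treatments ended in the window, for restart, switch and discontinuation.
- **Censoring:** treat patients whose observation ends before 180 days as censored, not as discontinued.
- **Exclusion:** replace the start-date exclusion with these rules.
- **Meningioma:** report cases on treatment per person-years on treatment.

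The cost is protocol wording and cohort dates in the code. Fewer post-period treatment ends contribute (62 days' worth in Germany at the listed lock), and reference years may differ by database.
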